7.1.2. Discontinuation of Study Drug

Study drug must be discontinued for an individual patient in the following instances:

- If an AE of Grade 3 or above based on National Cancer Institute (NCI) Common Terminology Criteria for Adverse Events (CTCAE) 5.0 occurs and is considered related to study drug as judged by the Investigator per the guidance in Appendix 6.
- Development of TSH level outside the normal range (confirmed by repeat testing) that is determined to be clinically significant or warrants initiation of new medications or therapies to treat thyroid dysfunction of signs of hyper/hypothyroidism. (Note: Dose adjustment of thyroid hormone replacement therapy with levothyroxine without discontinuing study drug may be allowed once after at least 6 weeks of study drug administration at Investigator's discretion upon consultation with Medical Monitor as referenced in Section 6.6).
- Necessary use of nonpermitted concomitant drug (ie. CYP3A4/P-gp/BCRP strong inhibitor/inducer) as referenced in Section 6.6.

Protocol TERNCB-2002 Terns, Inc.

- Symptoms of COVID-19 requiring hospitalization.
- Change in status that, in the judgement of the Investigator compromises the patient's ability to continue treatment or is not considered to be in the patient's best interest.
- Patient request to discontinue study drug for any reason.
- Pregnancy during the study (refer to Appendix 7).
- Sponsor discretion.
- Discontinuation of the study at the request of the Sponsor, a regulatory agency, or Institutional Review Board (IRB)/Independent Ethics Committee (IEC).

Study drug may be discontinued upon confirmation by repeat testing for an individual patient in the following instances at the discretion of the Investigator, and the Medical Monitor should be informed if any of the following occurs:

- If one of the following laboratory abnormalities is confirmed by repeat testing, considered related to the study drug and does not have alternative etiology (repeat test should be performed within 48-72 hours once initial abnormality is detected):
 - $\circ \quad \text{ALT or AST} > 8 \times \text{ULN}$
 - \circ ALT or AST > 5 × ULN for more than 1 week during study drug administration
 - ALT or $AST > 2 \times Baseline$ with the appearance of fatigue, nausea, vomiting, right upper quadrant pain or tenderness, fever, rash, and/or eosinophilia (> 5%)
 - \circ ALT or AST > 2 × Baseline and total bilirubin > 2 × ULN or INR > 1.5 for more than 1 week, confirmed with a repeat assessment
 - \circ ALP > 5 x ULN
 - \circ ALP > 3 x ULN and total bilirubin > 2x ULN

Study drug administration may not be resumed unless discussed and agreed with the Medical Monitor.

In addition, Investigators may permanently discontinue study drug at their discretion, for example, due to patient non-compliance with study drug or study assessments.

If study drug is permanently discontinued, the patient should remain in the study to be evaluated at the remaining visits through the Follow-Up visit; scheduled assessments may be performed at Investigator's discretion in consultation with Medical Monitor/Sponsor; PK samples will not be collected at subsequent visits after study drug discontinuation. See the Schedule of Activities for data to be collected at the time of discontinuation of study drug and follow-up and for any further evaluations that need to be completed.

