Appendix 3: Liver Chemistry Increased Monitoring Criteria

Table 10 summarizes requirements for follow-up of liver function test abnormalities.

 Table 10
 Liver Chemistry Increased Monitoring Criterion and Follow-Up

Criterion	Actions
Elevated ALT and/or AST: • Above 2 × Baseline, or	 Participant can continue study drug at the discretion of the Investigator
• Above 5 × ULN	 Repeat measurement of LFTs (including ALT, AST, ALP, and total bilirubin) will be performed within 48 hours to
Elevated ALP above 3 × ULN	confirm the abnormalities and to determine if they are increasing or decreasing. If total bilirubin is increased above the upper limit of normal, there should be a reflex to direct and indirect bilirubin.
	 PT/INR and albumin will be tested when significantly abnormal liver function is observed and repeated with repeat measurement of LFTs.
	 Upon confirmation of elevated LFTs, close observation by repeating LFTs every 24 to 72 hours will be initiated immediately.
	 Frequency of monitoring can be decreased as LFTs decrease at the Investigator's discretion.
	 The Investigator will collect detailed information on concomitant symptoms, new medications, drug or alcohol exposure, etc., to identify possible cause of abnormal LFTs.
	 Close observation on abnormal LFTs will last until the parameters return to baseline, or to a stable level judged by the Investigator.

Abbreviations: ALP = alkaline phosphatase; ALT = alanine transaminase; AST = aspartate transaminase; INR = international normalized ratio; LFT = liver function test; PT = prothrombin time; ULN = upper limit of normal

Note: If any of the following laboratory abnormalities is confirmed by repeat testing, considered related to the study drug and does not have alternative etiology, study drug may be discontinued at the discretion of the Investigator in accordance with Section 7.1.2, and the Medical Monitor should be informed (repeat test should be performed within 48-72 hours once initial abnormality is detected):

- $\circ \qquad \text{ALT or AST} > 8 \times \text{ULN}$
- $\circ~$ ALT or AST $>5\times$ ULN for more than 1 week during study drug administration
- ALT or AST > 2 × Baseline with the appearance of fatigue, nausea, vomiting, right upper quadrant pain or tenderness, fever, rash, and/or eosinophilia (> 5%)
- ALT or AST > 2 × Baseline and total bilirubin > 2 × ULN or INR > 1.5 for more than 1 week, confirmed with a repeat assessment
- \circ ALP > 5 x ULN

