Appendix 4: Fridericia's Formula

A single 12-lead ECG will be obtained as outlined in the Schedule of Activities (see Section 1.1) using an ECG machine that automatically calculates the heart rate and measures PR, QRS, and QT intervals. QTc will be calculated using Fridericia's Formula as outlined below.

The Investigator will review the ECGs for any clinically significant abnormalities.

Fridericia's Formula:

QTc = QT/(RR^0.33) http://www.thecalculator.co/health/QTc-Calculator-385.html

Appendix 5: Chronic Kidney Disease Epidemiology Collaboration (CKD-EPI) Formula to Estimate Glomerular Filtration Rate

 $GFR = 141 \times \min(S_{cr}/\kappa, 1)^{\alpha} \times \max(S_{cr}/\kappa, 1)^{-1.209} \times 0.993^{Age} \times 1.018 \text{ [if female]} \times 1.159 \text{ [if black]}$

Abbreviations / Units:

SCr (standardized serum creatinine) = mg/dL $\kappa = 0.7$ (females) or 0.9 (males) $\alpha = -0.329$ (females) or -0.411 (males) min = indicates the minimum of SCr/ κ or 1 max = indicates the maximum of SCr/ κ or 1 age = years

Appendix 6: Adverse Events: Definitions and Procedures for Recording, Evaluating, Follow-up, and Reporting

AE Definition

- An AE is any untoward medical occurrence in a patient or clinical study patient, temporally associated with the use of study drug, whether or not considered related to the study drug.
- NOTE: An AE can therefore be any unfavorable and unintended sign (including an abnormal laboratory finding), symptom, or disease (new or exacerbated) temporally associated with the use of study drug.

Events Meeting the AE Definition

- Any safety assessment (eg, ECG, radiological scans, vital signs measurements), including those that worsen from baseline, considered clinically significant in the medical and scientific judgment of the Investigator (ie, not related to progression of underlying disease).
- A clinical condition or symptom associated with an abnormal laboratory test result (e.g. hematology, clinical chemistry, or urinalysis). An abnormal laboratory test that is not accompanied with other signs or symptoms should not be reported as an AE.
- Exacerbation of a chronic or intermittent pre-existing condition including either an increase in frequency and/or intensity of the condition.
- New conditions detected or diagnosed after study drug administration even though it may have been
 present before the start of the study.
- Signs, symptoms, or the clinical sequelae of a suspected drug-drug interaction.

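### Stopping study drug stays optional for a confirmed, drug-attributed liver enzyme rise with raised bilirubin (or, for ALT/AST, raised INR), and the mandatory Grade 3+ adverse event rule may miss an asymptomatic case

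*Protocol*

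**What the plan says.** Protocol 7.1.2 has two lists. The first names situations in which drug must be stopped. It includes a related adverse event of Grade 3 or above, and a judgement-based item: "Change in status that, in the judgement of the Investigator compromises the patient's ability to continue treatment", extended to cases where continuing is not in the patient's interest. Sponsor discretion is also on this list.

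The second list holds every liver laboratory criterion and opens: "Study drug may be discontinued upon confirmation by repeat testing for an individual patient in the following instances at the discretion of the Investigator". It asks that the Medical Monitor be informed. Two of its items combine an enzyme with a sign of impaired liver function:

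- ALT or AST above twice baseline, with total bilirubin above 2×ULN or "INR > 1.5 for more than 1 week, confirmed with a repeat assessment"
- "ALP > 3 x ULN and total bilirubin > 2x ULN"

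Appendix 3, Table 10, covers ALT or AST above twice baseline or 5×ULN, and ALP above 3×ULN. Its first action is "Participant can continue study drug at the discretion of the Investigator". Once a rise is confirmed, "close observation by repeating LFTs every 24 to 72 hours will be initiated immediately". The note under the table repeats the discretionary wording of 7.1.2.

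Appendix 6 decides what counts as an adverse event. Its general note says "An AE can therefore be any unfavorable and unintended sign (including an abnormal laboratory finding", among other things. The list of qualifying events then says "An abnormal laboratory test that is not accompanied with other signs or symptoms should not be reported as an AE", and the list of non-qualifying events says the same again.

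**The concern.** The discretionary list already requires a confirming repeat test, a judgement of relatedness and no other cause. Discretion therefore remains after the clinical judgement has been made. By contrast, a confirmed TSH abnormality judged clinically significant is a mandatory stop in the same section.

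The patient at stake has a drug-attributed enzyme rise with raised bilirubin or INR and no symptoms. Entry criteria exclude total bilirubin above 1.2 mg/dL, and INR above 1.2 in patients not on anticoagulants, so such a pattern would generally be new on study. Section 2.3 reports liver enzyme elevation with both drug classes and says that neither TERN-501 nor the combination had been evaluated in NASH patients. SAP 7.3 plans no data monitoring committee. The study-level rules in 7.1.1 need, for Grade III events, three patients with the same related event.

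If the case is not recorded as an adverse event, it also drops out of the TEAE incidence endpoint (a secondary endpoint) and out of 24-hour SAE reporting, because Appendix 6 says an event that is not an AE cannot be an SAE.

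**Working it through.** The plan states no figure on this point, so there is none to reproduce. The check sets the texts side by side, then counts calendar days.

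**1. Must or may (7.1.2).** The mandatory list has 9 bullets: related Grade 3+ AE, TSH, prohibited co-medication, COVID-19 hospitalization, change in status, patient request, pregnancy, Sponsor discretion and study termination. None (0 of 9) names ALT, AST, ALP, bilirubin or INR. All 6 liver laboratory criteria are on the optional list, including both combined ones. The only mandatory route tied to a severity grade is the related Grade 3+ AE rule, and it works only if the case is first an AE.

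**2. Is an asymptomatic laboratory-only case an AE? (Appendix 6)**

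| Text | Direction |
|---|---|
| General note: an abnormal laboratory finding can be an AE | AE |
| Safety assessments that worsen from baseline and are judged clinically significant | AE |
| Conditions newly detected or diagnosed after dosing | AE |
| Instruction to record the diagnosis rather than its individual signs | AE, if a diagnosis is made |
| Laboratory abnormality without signs or symptoms, in the qualifying-events list | Not an AE |
| The same, in the non-qualifying list | Not an AE |

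Section 8.1.9 sends the Investigator back to Appendix 6, so it does not settle the matter. One site could diagnose drug-induced liver injury, grade it, stop drug and report it. Another could record laboratory values only and continue. Both could cite the protocol.

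**3. What the SAP would still show.** A bilirubin case (above 2×ULN) is counted in the total bilirubin rows of SAP Table 11. An INR-only case appears in the ALT/AST rows if the enzyme reaches 3×ULN. A value just over twice baseline stays below that when baseline is under 1.5×ULN (2 × 1.5 = 3). Coagulation is not summarized (SAP 8.3) but is listed by patient (SAP 9). The only thing not tabulated is the enzyme-plus-INR combination.

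**4. Maximum further dosing.** Inputs are the nominal visit days 15, 29, 43 and 57 and the last dosing day, 85 (Schedule of Activities). Remaining days = 85 − (visit day + k), where k is the number of days from the visit at which the abnormality appears to the criterion being met.

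- k = 3 applies to a 72-hour confirmation, the outer limit in 7.1.2.
- k = 8 applies if the phrase about more than one week governs the whole ALT/AST item and not INR alone, since day 7 is not yet more than a week.

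| First seen | k = 3 | Share of 85 days | k = 8 | Share of 85 days |
|---|---|---|---|---|
| Week 2 (Day 15) | 85 − 18 = 67 | 78.8% | 85 − 23 = 62 | 72.9% |
| Week 4 (Day 29) | 85 − 32 = 53 | 62.4% | 85 − 37 = 48 | 56.5% |
| Week 6 (Day 43) | 85 − 46 = 39 | 45.9% | 85 − 51 = 34 | 40.0% |
| Week 8 (Day 57) | 85 − 60 = 25 | 29.4% | 85 − 65 = 20 | 23.5% |

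The two readings differ by 8 − 3 = 5 days. A 48-hour confirmation (k = 2) adds one day to each k = 3 figure.

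**The case against.** The strongest reply is that an Investigator who has confirmed the abnormality, attributed it to the drug and found no other cause would hardly judge further dosing to be in the patient's interest, so the mandatory best-interest bullet already applies. The Sponsor can also stop drug in any patient, the Medical Monitor should be told, liver tests are not among the blinded analytes, and 7.1.1 provides regular blinded review of laboratory values. All of this is true, and most investigators would probably stop. These safeguards still rest on judgement and contain no threshold. None obliges a stop at these values.

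A second reply is that Appendix 6 favors recording such a case: an enzyme-plus-bilirubin pattern attributed to the drug is more naturally a diagnosis than a bare test result. That narrows the conflict. It does not remove two explicit exclusions that make no exception for liver tests or for clinical significance.

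A third is that section 2.3 reports no drug-induced liver injury with either drug. This bears on how likely a case is, and no likelihood is claimed here.

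A fourth is that the proposed stop still depends on the Investigator's causality judgement, and that twice baseline has no ULN floor and can be a modest value. Both are fair. The change removes only the option to continue once causality has been accepted. The bilirubin or INR limb, with the three preconditions, limits how often a modest enzyme value would force a stop.

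**Conclusion.** The concern holds as a participant-safety gap worth closing. Following the plan as written, an asymptomatic, drug-attributed case meeting either combined criterion may stay on drug and may go unrecorded as an AE. The ceiling on further dosing is 67, 53, 39 or 25 days, or 62, 48, 34 or 20 days under the longer reading of the ALT/AST item. These ceilings assume nominal visit days and uninterrupted dosing under Table 10 monitoring. They are not expected exposure. No sample size or power figure is affected.

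A reader might infer four stronger things that the documents do not support:

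- **That no mandatory route could apply.** The best-interest bullet, Sponsor discretion and the Grade 3+ rule all could.
- **That Appendix 6 plainly excludes these cases.** It conflicts with itself. A symptomatic case can be recorded as an AE and can then fall under the Grade 3+ rule.
- **That an INR-only case disappears from the analysis.** Its enzymes appear in SAP Table 11 from 3×ULN, and its INR appears in the listings.
- **That harm is likely.** The documents give no event rate from which to estimate a case probability.

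**What to change.** 1. **Protocol 7.1.2.** Move the two combined criteria to the mandatory list, to apply once confirmed by repeat test, considered related and without another cause. Write the first as *ALT or AST >2× Baseline and (total bilirubin >2×ULN or INR >1.5)*, with the one-week phrase deleted. The second is ALP >3×ULN with total bilirubin >2×ULN. State that isolated ALT, AST or ALP elevations, and the item for ALT/AST with symptoms, stay discretionary. A symptomatic case can be recorded as an AE and reach the Grade 3+ rule that way.
2. **Appendix 6.** State that an abnormality meeting either combined criterion is recorded as an AE with a causality assessment, whether or not there are symptoms, and is reported to the Sponsor within 24 hours.
3. **Appendix 3, Table 10.** Reword the first action to *can continue study drug unless a mandatory criterion in 7.1.2 is met*.

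The cost is a short amendment with a site notification, and possibly a few more discontinuations. No visits or tests are added, because Table 10 already requires the repeat liver tests and PT/INR.

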7.2. Patient Discontinuation/Withdrawal from the Study

A patient may withdraw from the study at any time at his/her own request or may be withdrawn at any time at the discretion of the Investigator for safety, behavioral, compliance, or administrative reasons.

Patients discontinuing the study at any time for any reason (Early Termination [ET]) should complete the ET visit as soon as feasible and return for a Follow-Up approximately 4 weeks after the last dose of study drug. See the Schedule of Activities for data to be collected at the time of study discontinuation and follow-up and for any further evaluations that need to be completed.

If the patient withdraws consent for disclosure of future information, the Sponsor may retain and continue to use any data collected before such a withdrawal of consent.

If a patient withdraws from the study, he/she may request destruction of any samples taken and not tested, and the Investigator must document this in the site study records.

7.3. Lost to Follow up

A patient will be considered lost to follow-up if he or she repeatedly fails to return for scheduled visits and is unable to be contacted by the study site.

The following actions must be taken if a patient fails to return to the clinic for a required study visit:

- The site must attempt to contact the patient and reschedule the missed visit as soon as possible, counsel the patient on the importance of maintaining the assigned visit schedule and ascertain whether or not the patient wishes to and/or should continue in the study.
- Before a patient is deemed lost to follow up, the Investigator or designee must make every effort to regain contact with the patient (where possible, 3 telephone calls and, if necessary, a certified letter to the patient's last known mailing address or local equivalent methods). These contact attempts should be documented in the patient's medical record.
- Should the patient continue to be unreachable, he/she will be considered to have withdrawn from the study.

Discontinuation of specific sites or of the study as a whole are addressed in Section 10.1.8 and Section 7.1.1.

8. Study Assessments and Procedures

Study procedures and their timing are summarized in the Schedule of Activities. Protocol waivers or exemptions are not allowed.

Adherence to the study design requirements, including those specified in the Schedule of Activities, is essential and required for study conduct.

All screening evaluations must be completed and reviewed to confirm that potential patients meet all eligibility criteria. The Investigator will maintain a screening log to record details of all patients screened and to confirm eligibility or record reasons for screening failure, as applicable.

Repeat or unscheduled samples may be taken for safety reasons or for technical issues with the samples.

If a patient requires home quarantine due to SARS-CoV-2 infection or exposure, or due to COVID-19 symptoms or other associated concern with attending an in-person study visit, in accordance with Section 6.8.1, home health care visits may be made available to continue study assessments in the patient's home where feasible, and/or remote visits via telephone, telemedicine, or other appropriate virtual communication may be substituted for a visit to the site.

8.1. Study Assessments

Planned time points for all safety assessments are provided in the Schedule of Activities (Section 1.3).

8.1.1. Demographics

Demographic data includes age (year of birth), sex, race, and ethnicity.

8.1.2. Height and Weight

Height and weight are collected at Screening and will be used to calculate BMI for eligibility. Only weight is collected at Weeks 0, 6, 12, 16, and ET.

8.1.3. Medical History

Medical history including details of illnesses, allergies, or procedures including liver biopsy, date(s) of onset, whether condition(s) is currently ongoing, medication history, including alcohol use, will be collected for all patients at Screening and prior to Randomization.

8.1.4. Physical Examinations

A complete physical examination be performed at Screening, Week 16, and ET and will include assessments of general appearance, cardiovascular, respiratory, abdomen, head and neck (including ears, eyes, nose and throat), lymph nodes, thyroid, and musculoskeletal systems.

A targeted physical examination will be conducted at all other study visits as needed, based on clinical judgement of the Investigator, to evaluate reported current or prior AEs, symptoms reported by the patient, or abnormal laboratory readouts.

Investigators should pay special attention to clinical signs related to previous serious illnesses.

8.1.5. Vital Signs

Temperature, pulse rate, respiratory rate, and blood pressure will be assessed at all study visits as outlined in the Schedule of Activities (Section 1.3) and maintained in source documentation.

Blood pressure and pulse measurements will be assessed with a completely automated device. Manual techniques will be used only if an automated device is not available.

Blood pressure and pulse measurements should be preceded by at least 5 minutes of rest for the patient in a quiet setting without distractions (eg, television, cell phones).

8.1.6. Electrocardiograms

Single 12-lead ECGs will be obtained at all study visits as outlined in the Schedule of Activities (Section 1.3) using an ECG machine that automatically calculates the heart rate and measures PR, QRS, and QT intervals. QTc will be calculated using the formula outlined in Appendix 4.

In the instance of patient-reported symptoms considered potentially cardiac in nature such as chest pain/pressure, palpitations, dizziness, shortness of breath, or report of patient recently seeking medical care for such symptoms (e.g., emergency room visit), perform an an-hoc ECG, and, per the clinical judgement of the Investigator, obtain cardiology consult as needed.

Participants will be instructed to lie supine for at least 10 minutes prior to 12-lead ECG collection. During ECG collection, participants should be in a quiet setting, without distractions, and refrain from talking or moving their arms or legs.

The Investigator will review the ECGs for any clinically significant abnormalities.

